2.3 ANALYSIS POPULATIONS

Patients treated without being randomized will not be considered randomized and will not be included in any efficacy population.

The randomized population includes any patient who has been allocated to a randomized treatment regardless of whether the treatment kit was used.

For any patient randomized more than once in Part 2 (with two different patient ID), with first randomization being by error, only the data associated with the second patient ID (without randomization code error) will be used in any analysis population.

The safety experience of patients treated and not randomized will be reported separately, and these patients will not be in the safety population.

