2.3.2 Safety population

The Safety populations considered for safety analyses will be the randomized population who did actually receive at least one dose or part of a dose of the double-blind IMP. Patients will be analyzed according to the treatment actually received.

Part 1: Dose escalation phase

Safety data in Part 1 will be described separately for non-Japanese and Japanese patients:

- The Part 1 non-Japanese safety population will be defined as all non-Japanese patients randomized in Part 1 who received at least 1 dose of study medication in Part 1 of the study. All safety analyses in non-Japanese Part 1 of the study will be performed on the Part 1 non-Japanese safety population
- The Part 1 Japanese safety population will be defined as all Japanese patients randomized in Part 1 who received at least 1 dose of study medication in Part 1 of the study. All safety analyses in Japanese Part 1 of the study will be performed on the Part 1 Japanese safety population

In addition:

- Nonrandomized but treated patients will not be part of the safety population; however, their safety data will be presented separately

- Randomized patients for whom it is unclear whether they took the IMP will be included in the safety population as randomized
- For patients receiving more than 1 study treatment within the same part of the study, the treatment group allocation for as-treated analysis will be the one to which the patient was treated with the longest duration.

Part 2: Treatment phase

The Part 2 safety population will be defined as all randomized patients in Part 2 who received at least 1 dose of study medication in Part 2 of the study. Patients from Part 1 who are re-randomized in Part 2 will not be included in Part 2 safety population, and will be described separately. Safety analyses of the 52-week blinded treatment period of Part 2 of the study will be performed on the Part 2 safety population.

The Part 2 LTFU safety population will be defined as patients who participated to the long-term follow-up period and received at least 1 dose of GZ/SAR402671 after the Week 52 visit. Safety analyses of the long-term follow-up period of Part 2 of the study will be performed on the Part 2 LTFU safety population.

In addition:

- Nonrandomized but treated patients will not be part of the safety population; however, their safety data will be presented separately

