- Randomized patients for whom it is unclear whether they took the double-blind IMP will be included in the safety population as randomized
- For patients receiving more than 1 double-blind IMP within the same part of the study, the treatment group allocation for as-treated analysis will be the one to which the patient was treated with the longest duration.

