2.4.3 Extent of investigational medicinal product exposure and compliance

The extent of IMP exposure and compliance will be assessed and summarized by actual treatment within the safety population ([Section 2.3.2](#)), separately for Part 1 and Part 2 of the study. In Part 1, data will be presented separately for Japanese and non-Japanese patients.

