2.4.5 Analyses of safety data

Safety analyses will be performed on the safety populations (see [Section 2.3.2](#)), separately for Part 1 and Part 2 of the study. In Part 1, data will be presented separately for Japanese and non-Japanese patients.

In Part 2, safety data will be presented separately for the two following periods:

- Safety analysis of the 52-week blinded treatment period of Part 2. This analysis will present safety data collected up to the Week 52 visit (or end of treatment visit in case of premature treatment discontinuation before Week 52). Safety analyses will present safety data from the two treatment arms:
 - Placebo
 - GZ/SAR402671 15mg

- Safety analysis of the 104-week long-term follow-up period of Part 2. This analysis will present safety data collected from the Week 52 visit to the end of study, excluding the initial 52-week blinded treatment period. Only patients having received GZ/SAR402671 15mg during the long-term follow-up period will be included in this analysis. Safety analyses will present safety data from the following groups:
 - Delayed start: patients having received placebo during the 52-week treatment period, then having received GZ/SAR402671 during the long-term follow-up period.
 - Early start: patients having received GZ/SAR402671 during the 52-week treatment period, then having continued to receive GZ/SAR402671 during the long-term follow-up period.
 - All patients: all patients having received GZ/SAR402671 during the long-term follow-up period
- Safety analysis of the overall GZ/SAR402671 treatment period in Part 2. This analysis will present all safety data collected from the first intake of GZ/SAR402671 in Part 2 to the last intake of GZ/SAR402671 in Part 2 plus 6 weeks. All patients having received GZ/SAR402671 15mg in Part 2 (either during the 52-week blinded treatment period or during the long-term follow-up period) will be included in this analysis. Safety analyses will present safety data from the following group:
 - Overall GZ/SAR402671: patients having received GZ/SAR402671 during the 52-week treatment period and/or during the long-term follow-up period.

Details of timing of these two analyses is presented in [Section 4](#).

General common rules

The safety analysis will be conducted according to the Sanofi document BTD-009536 (version applicable at the time of database lock) “Analysis and reporting of safety data from Clinical Trials through the Clinical Study Report.”

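### For a patient randomized twice in Part 2, the first time by error, the second-ID-only rule extends to the safety population with no exception for IMP taken under the first ID

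*SAP*

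**What the plan says.** SAP section 2.3 covers a patient who is randomized more than once in Part 2 under two different IDs, "with first randomization being by error". For that patient "only the data associated with the second patient ID (without randomization code error) will be used in any analysis population".

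The same section treats a neighbouring group differently: "The safety experience of patients treated and not randomized will be reported separately".

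Section 2.3.2 defines the Part 2 safety population as "all randomized patients in Part 2 who received at least 1 dose of study medication in Part 2 of the study", and patients in the safety population are analyzed by the treatment they actually received. It adds a rule "For patients receiving more than 1 double-blind IMP within the same part of the study": as-treated allocation follows whichever product was taken longest.

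Sections 2.4.3 and 2.4.5 tie the outputs to that population: "The extent of IMP exposure and compliance will be assessed and summarized by actual treatment within the safety population", and "Safety analyses will be performed on the safety populations". Section 2.4.5.1 uses the same population as the denominator for adverse event percentages.

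**The concern.** Keeping one record per patient is sensible for efficacy, where an erroneous allocation should not be counted twice. Safety analysis has a different purpose: it describes what happened to people who took the drug, however they came to take it. A rule that removes the first-ID record from every population also removes any dosing under that ID, and with it the events and abnormalities that followed.

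At stake is the completeness of the safety and exposure tables for these patients. New or worsening lens opacity and ALT increase are events of special interest (section 2.1.4.1), and when such events are few a single one can matter. Programming consistency is also at stake: one programmer following section 2.3 and another following section 2.3.2 could place the same patient's data differently.

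**Working it through.** **1. Reach of the rule.** Section 2.3 names any analysis population, and section 2.3.2 is one of its subsections, so safety is included. There are two conditions: two IDs in Part 2, and a first randomization made in error. Dosing is not a condition. Sections 2.2 and 2.3 count a patient as randomized once treatment has been allocated, whether or not the kit was used. Dosed and undosed patients therefore both fall under the rule.

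**2. The possible cases.**

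| IMP under first ID | IMP under second ID | Result under section 2.3 |
|---|---|---|
| No | Yes or no | Nothing is lost |
| Yes | Yes | Patient is in the safety population through the second ID; first-ID exposure and safety data are not used |
| Yes | No | Second-ID data show no dose, so the patient drops out of the safety tables |

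**3. Compare with section 2.3.2.** In the third case, section 2.3.2 would place the patient in the safety population, because the patient was randomized and received at least one dose in Part 2. In the second case, if the two courses were different treatments, the longest-duration rule needs the dosing dates from both IDs, and section 2.3 sets one set aside. The pooled analysis of all GZ/SAR402671 exposure in section 2.4.5 is affected in the same way. It starts at the first intake of the drug in Part 2, which could be an intake under the first ID.

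**4. Look for a provision that recovers the data.**
- Separate reporting in sections 2.3 and 2.3.2 is for patients treated without being randomized. This patient was randomized.
- The common rules in section 2.4.5 list safety data for patients outside the safety population. That may catch the third case. It does not clearly catch the second, because that patient is inside the population through the second ID.
- Section 2.2.1 has the irregularity documented in the study report. It does not mention the associated adverse event or exposure data.

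**5. Size.** The only relevant design figure is the arm size in section 1.3.2: 108 per arm, from a difference of 4.06, an SD of 10.01, two-sided alpha of 0.05, 80% power and about 10% loss.
- Normal approximation: n = 2 × (1.960 + 0.842)² × (10.01/4.06)² = 2 × 7.85 × 6.08 = 95.4, so 96 per arm. Then 96/0.9 = 106.7, so 107.
- With the t distribution, 96 per arm gives power 0.798 and 97 gives 0.802. Then 97/0.9 = 107.8, so 108. The stated figure reproduces.
- One patient with an event missing from an arm of 108: 1/108 = 0.93 percentage points.

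The SAP gives no count of patients randomized twice and no count of those dosed under a first ID, so an expected effect cannot be calculated.

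**The case against.** The strongest reply is that the rule is narrow and probably harmless. It applies only where the first randomization was an error, and section 2.2.1 lists such errors among allocation irregularities. Many would be caught before any dose, and then nothing is lost. A specific rule at the head of section 2.3 can also be read as qualifying the general definitions below it. The longest-duration rule keeps a clear use without it, for a patient dispensed a kit other than the one assigned. Adverse events are still collected from consent to the end of the study, so the records exist.

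Most of that stands. The sections are in tension rather than in flat contradiction, and the defect is a missing exception. What the reply does not answer is the patient dosed under both IDs: the first-ID data are excluded from the tables and no listing clearly covers them.

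A reader might also infer more than the SAP supports:
- **Loss related to outcome.** One might picture a patient who stops because of an event, is re-entered and loses that event. The trigger is an erroneous randomization, not a stopped course, so that scenario lies largely outside the rule.
- **Active-drug effects counted under placebo.** This would need first-ID dosing, different treatments under the two IDs, and a short gap or a delayed effect. Section 2.4.4.1 equates 7 days with about five half-lives. Nothing in the SAP shows that these conditions occur together.
- **A baseline taken after exposure.** Section 2.1.1 sets baseline at or before the first double-blind IMP administration and does not mention IDs. A post-exposure baseline is a possible consequence of using second-ID data only, not something the SAP states.

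**Conclusion.** The point holds in limited form. As written, the rule gives an incomplete safety and exposure analysis for any patient who was randomized twice in Part 2 under two IDs, the first time in error, and who took IMP under the first ID. In that situation it conflicts in effect with the dosing-based definition and the longest-duration allocation in section 2.3.2.

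The number of such patients is not given and may be zero. The figure of 0.93 percentage points per omitted patient assumes that all 108 planned patients in the arm are treated, that the patient stays in that arm's denominator, and that the event is not also recorded under the second ID. The efficacy analyses are not part of this concern. The reason to act is that a stated rule drops safety data from exposed patients and the correction is simple.

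**What to change.** Limit the second-ID-only sentence in section 2.3 to the efficacy populations. For safety and exposure, add a rule for patients who took any IMP under the first ID, choosing one of two options:

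1. Link the two IDs as one patient, include safety and exposure data from the first Part 2 dose onward, take baseline before that dose, and allocate the arm by the existing longest-duration rule in section 2.3.2. Assigning each event to the treatment being taken at onset would introduce a new conflict with that rule, so it is not proposed.
2. Keep the second-ID data in the tables and list the first-ID safety data separately, as is done for patients treated without randomization.

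Where no IMP was taken under the first ID, the present rule can stand. Option 1 gives complete tables. Option 2 is simpler, but the tables stay incomplete and the reader has to consult the listing. The cost is a few sentences in the SAP and, for any affected patients, a manual link between two IDs.

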2.3.1 Efficacy populations

Part 1: Dose escalation phase

Exploratory efficacy endpoints in Part 1 of the study will be described separately for non-Japanese and Japanese patients:

- The Part 1 non-Japanese ITT population will be defined as all non-Japanese patients randomized in Part 1. Patients will be analyzed in the treatment group to which they were randomized
- The Part 1 Japanese ITT population will be defined as all Japanese patients randomized in Part 1. Patients will be analyzed in the treatment group to which they were randomized

Part 2: Treatment phase

The Part 2 intent-to-treat (ITT) population will be defined as all randomized patients in Part 2. Patients will be analyzed in the treatment group to which they were randomized

Patients from Part 1 who are rerandomized in Part 2 will not be included in Part 2 ITT population and will be described separately. The Part 2 ITT population is the primary analysis population for all efficacy endpoints.

2.3.2 Safety population

The Safety populations considered for safety analyses will be the randomized population who did actually receive at least one dose or part of a dose of the double-blind IMP. Patients will be analyzed according to the treatment actually received.

Part 1: Dose escalation phase

Safety data in Part 1 will be described separately for non-Japanese and Japanese patients:

- The Part 1 non-Japanese safety population will be defined as all non-Japanese patients randomized in Part 1 who received at least 1 dose of study medication in Part 1 of the study. All safety analyses in non-Japanese Part 1 of the study will be performed on the Part 1 non-Japanese safety population
- The Part 1 Japanese safety population will be defined as all Japanese patients randomized in Part 1 who received at least 1 dose of study medication in Part 1 of the study. All safety analyses in Japanese Part 1 of the study will be performed on the Part 1 Japanese safety population

In addition:

- Nonrandomized but treated patients will not be part of the safety population; however, their safety data will be presented separately

- Randomized patients for whom it is unclear whether they took the IMP will be included in the safety population as randomized
- For patients receiving more than 1 study treatment within the same part of the study, the treatment group allocation for as-treated analysis will be the one to which the patient was treated with the longest duration.

Part 2: Treatment phase

The Part 2 safety population will be defined as all randomized patients in Part 2 who received at least 1 dose of study medication in Part 2 of the study. Patients from Part 1 who are re-randomized in Part 2 will not be included in Part 2 safety population, and will be described separately. Safety analyses of the 52-week blinded treatment period of Part 2 of the study will be performed on the Part 2 safety population.

The Part 2 LTFU safety population will be defined as patients who participated to the long-term follow-up period and received at least 1 dose of GZ/SAR402671 after the Week 52 visit. Safety analyses of the long-term follow-up period of Part 2 of the study will be performed on the Part 2 LTFU safety population.

In addition:

- Nonrandomized but treated patients will not be part of the safety population; however, their safety data will be presented separately
- Randomized patients for whom it is unclear whether they took the double-blind IMP will be included in the safety population as randomized
- For patients receiving more than 1 double-blind IMP within the same part of the study, the treatment group allocation for as-treated analysis will be the one to which the patient was treated with the longest duration.

2.3.3 Pharmacokinetics population

The PK population will be defined as all patients who received at least 1 dose of GZ/SAR402671 and who have at least one PK assessment.

Part 1: Dose escalation phase

Pharmacokinetics data in Part 1 will be described separately for non-Japanese and Japanese patients:

- The Part 1 non-Japanese PK populations will be defined as all non-Japanese patients randomized in Part 1 who received at least 1 dose of GZ/SAR402671 and who have at least one PK assessment
- The Part 1 Japanese PK populations will be defined as all Japanese patients randomized in Part 1 who received at least 1 dose of GZ/SAR402671 and who have at least one PK assessment

Part 2: Treatment phase

The Part 2 PK population will be defined as all patients randomized in Part 2 who received at least 1 dose of GZ/SAR402671 and who have at least one PK assessment.

Patients from Part 1 who are rerandomized in Part 2 will not be included in Part 2 PK population, and will be described separately.

2.3.4 Pharmacodynamic population

The pharmacodynamic population will be defined as all patients who received at least 1 dose of the double-blind IMP and who have at least one pharmacodynamics assessment.

Part 1: Dose escalation phase

Pharmacodynamics data in Part 1 will be described separately for non-Japanese and Japanese patients:

- The Part 1 non-Japanese pharmacodynamics populations will be defined as all non-Japanese patients randomized in Part 1 who received at least 1 dose of double-blind IMP and who have at least one pharmacodynamics assessment
- The Part 1 Japanese pharmacodynamics populations will be defined as all Japanese patients in Part 1 who received at least 1 dose of double-blind IMP and who have at least one pharmacodynamics assessment

Part 2: Treatment phase

The Part 2 pharmacodynamics populations will be defined as all patients randomized in Part 2 who received at least 1 dose of GZ/SAR402671 and who have at least one pharmacodynamics assessment.

Patients from Part 1 who are rerandomized in Part 2 will not be included in Part 2 pharmacodynamics population, and will be described separately.

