2.4.6 Analyses of pharmacokinetic and pharmacodynamic variables

Pharmacokinetic and pharmacodynamic variables will be presented for the Pharmacokinetics and pharmacodynamic populations respectively (see [Section 2.3.3](#) and [Section 2.3.4](#)), separately for Part 1 and Part 2 of the study. In Part 1, data will be presented separately for Japanese and non-Japanese patients.

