2.4.6.1 Analyses of pharmacodynamic variables

Pharmacodynamic data will be described separately for Part 1 and Part 2 of the study, and separately for Japanese and non-Japanese patients. Data of patients from Part 1 who are rerandomized in Part 2 will not be included in Part 2 and will be presented separately.

Part 1: Dose escalation phase

For all pharmacodynamics parameters, raw data and percent change from baseline will be summarized in descriptive statistics by treatment group and scheduled time of measurement for each population separately (Japanese and non-Japanese patients). No formal statistical comparison will be made.

Additionally, graphs over time will be presented plotting mean +/- SD by treatment group for each population separately (Japanese and non-Japanese patients).

Part 2: Treatment phase

In Part 2, pharmacodynamics data will be presented separately for the two following periods:

- Analysis of the 52-week blinded treatment period of Part 2. This analysis will present pharmacodynamics data from baseline to 52 weeks. Pharmacodynamic analyses will compare the two treatment arms:
 - Placebo
 - GZ/SAR402671 15mg
- Analysis of the 156-week treatment period. This analysis will present all pharmacodynamics data from baseline to 156 weeks, combining the 52-week blinded treatment period and the 104-week long-term follow-up period. Pharmacodynamic analyses will compare the two treatment strategies:
 - Delayed start: patients randomized to receive placebo for 52 weeks, then GZ/SAR402671 15mg for 104 weeks.
 - Early start: patients randomized to receive GZ/SAR402671 15mg for 52 weeks, then continued GZ/SAR402671 15mg for 104 weeks.

Percent change from baseline to Week 26 and Week 52 in plasma GL-1 will be analyzed using a MMRM including data available at Week 2, Week 4, Week 13, Week 26, Week 39 and Week 52 analysis time windows (as defined in Table 6). The model will include the fixed categorical effects of treatment group (GZ/SAR402671 versus placebo), randomization strata (use of levodopa/PD medication: yes/no, MoCA score <26: yes/no and severe GBA mutation: yes/no), time point (as defined in Table 6), treatment-by-time point interaction, randomization strata-by-time point interaction as well as the continuous fixed covariates of baseline and the baseline-by-time point interaction

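### SAP Section 2.3.4 contradicts itself: the Part 2 pharmacodynamic population requires a dose of GZ/SAR402671, which removes or selects the placebo arm of the GL-1 comparisons

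*SAP*

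**What the plan says.** Section 2.3.4 opens with a general definition of the pharmacodynamic population: "all patients who received at least 1 dose of the double-blind IMP and who have at least one pharmacodynamics assessment". The two Part 1 definitions (non-Japanese and Japanese) keep that dosing condition. The Part 2 definition does not: "The Part 2 pharmacodynamics populations will be defined as all patients randomized in Part 2 who received at least 1 dose of GZ/SAR402671", together with at least one pharmacodynamic assessment. This is the dosing condition of the Part 2 PK population in Section 2.3.3: "The Part 2 PK population will be defined as all patients randomized in Part 2 who received at least 1 dose of GZ/SAR402671".

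Section 2.4.6 ties the analyses to these populations: "Pharmacokinetic and pharmacodynamic variables will be presented for the Pharmacokinetics and pharmacodynamic populations respectively". For the 52-week blinded period, Section 2.4.6.1 states: "Pharmacodynamic analyses will compare the two treatment arms", and lists placebo and GZ/SAR402671 15 mg. It then specifies two models, each with a treatment-group effect of GZ/SAR402671 versus placebo:

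- Plasma GL-1: "Percent change from baseline to Week 26 and Week 52 in plasma GL-1 will be analyzed using a MMRM", using data from Weeks 2, 4, 13, 26, 39 and 52.
- CSF GL-1: an ANCOVA of percent change at Week 52.

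Under Sections 2.4.3.1 and 2.4.4, patients randomized to placebo receive GZ/SAR402671 in the 104-week long-term follow-up, after the 52 blinded weeks.

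**The concern.** A placebo-controlled comparison needs a population that placebo patients can enter because they were randomized and dosed. The Part 2 rule admits a placebo patient only through exposure to the active drug, which the design gives after the comparison period has ended. The rule therefore conflicts both with the general definition in its own section and with the analyses it is meant to serve.

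What is at stake is the randomized estimate of GL-1 response in plasma and CSF, a Part 2 secondary objective (Section 1.2.2.2), and the other Part 2 pharmacodynamic summaries by arm. If the rule is followed, the contrast either cannot be estimated or sets all dosed GZ/SAR402671 patients against a selected subset of placebo patients. If the analyst quietly uses another population, the analysis departs from the pre-specified rule.

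**Working it through.** **The plan's own arm size.** Section 1.3.2 gives 108 per arm from a difference of 4.06, an SD of 10.01, two-sided alpha 0.05, 80% power and about 10% early terminations or unevaluable patients.

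- Standardized effect: 4.06 / 10.01 = 0.406.
- A two-sample t-test needs 96.4, so 97 evaluable patients per arm.
- Inflation: 97 / (1 − 0.10) = 107.8, so 108. The stated figure reproduces.

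The figure serves here only as the planned size of the placebo arm.

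**Who qualifies under the Part 2 sentence.** Assume for simplicity that all 108 placebo patients are dosed and have a pharmacodynamic assessment, and set dispensing errors aside.

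*Reading A: the qualifying dose must fall in the 52-week blinded period.* No placebo patient takes GZ/SAR402671 in that period. Placebo n = 0, and the treatment effect in both GL-1 models cannot be estimated.

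*Reading B: any GZ/SAR402671 dose in Part 2 counts, including long-term follow-up.* Placebo n = 108 × f, where f is the share of placebo patients who took active drug in follow-up. The SAP gives no value for f, so the range below is assumed:

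| f | Placebo patients kept | Placebo patients lost |
|---|---|---|
| 0.5 | 54 | 54 |
| 0.8 | 86 | 22 |
| 0.9 | 97 | 11 |

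**What kind of loss Reading B causes.**

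- A placebo patient who stopped early and never took active drug is excluded, together with any plasma GL-1 values from Week 2 to Week 39. A GZ/SAR402671 patient who stopped early stays in. The two arms are thus selected by different rules, one of them acting after randomization.
- Section 4 sets the first-step cut-off at the date the last Part 2 patient completes the Week 52 visit. Placebo patients who reach Week 52 close to that date may not yet have taken an active dose. Membership then depends on the cut-off, and could differ between the first-step and the Week 156 analyses of the same blinded-period data.

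**After correction.** With a dose of double-blind IMP as the condition, every dosed placebo patient with an assessment qualifies, up to 108, whatever happens after Week 52.

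**The case against.** The strongest reply is that the intent is plain. The section's opening sentence admits placebo patients, Section 2.4.6.1 names placebo as an arm, and both models carry a placebo level, so the Part 2 sentence looks like a slip carried over from the PK definition. That is probably right, and it is why the remedy is small. It does not remove the problem, because the Part 2 sentence is the more specific rule. An empty placebo arm would be noticed at programming, but under Reading B the models run and nothing signals the exclusion.

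A second reply is that GL-1 changes are listed among the exploratory efficacy endpoints (Section 2.1.3.3) and that Section 2.3.1 makes the Part 2 ITT population primary for all efficacy endpoints. This shows a further ambiguity but does not override Section 2.4.6, which explicitly assigns pharmacodynamic variables to the pharmacodynamic population.

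A third reply concerns weight, and it stands. GL-1 is not among the secondary endpoints in Section 2.1.3.2, it is outside the hierarchy of Section 2.4.4.4, and p-values for exploratory endpoints are descriptive there.

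Two stronger inferences are tempting and are not supported:

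- A reader might infer that the same condition in Section 2.3.3 lets placebo samples, set to zero below the assay limit, dilute the Part 2 PK means, since Section 2.4.6.2 mentions summaries only by visit. Section 2.5.8 says plasma concentrations and PK parameters are summarized by treatment group, so that pooling is not what the SAP prescribes.
- A reader might take the 10% allowance in Section 1.3.2 as fixing f at no more than 0.9. That allowance covers early terminations and unevaluable patients in the sample size. It is not a rate of entry into follow-up, so 97 is an illustration and not a bound.

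**Conclusion.** The inconsistency is real and lies within one section. Followed literally, the Part 2 sentence gives the GL-1 comparisons either no placebo patients or 108 × f of them, selected by a post-randomization event and by the cut-off date. The direction and size of any bias cannot be derived from the SAP, because neither f nor its relation to GL-1 is given.

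The effect is confined to the Part 2 GL-1 analyses and the other Part 2 pharmacodynamic summaries. The MDS-UPDRS primary analysis and the three secondary efficacy endpoints use the ITT population and do not change. A reader might infer that a confirmatory conclusion is at risk; none is. The point should be fixed because it bears on a stated secondary objective and the written rule would give a wrong result, but the trial's main conclusion does not depend on it.

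This rests on placebo patients receiving GZ/SAR402671 only in long-term follow-up, and on Section 2.4.6 governing the population for the GL-1 models.

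**What to change.** In the Part 2 paragraph of Section 2.3.4, replace the condition of at least 1 dose of GZ/SAR402671 with at least 1 dose of the double-blind IMP in Part 2. Keep the requirement of a pharmacodynamic assessment and the exclusion of re-randomized Part 1 patients. The Part 2 rule then agrees with the general and Part 1 definitions and with the models in Section 2.4.6.1. No change to Section 2.3.3 is needed on this account.

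The cost is one phrase in the SAP, with no new data, visits or patients. It should be made before treatment codes are opened for the first-step analysis, so that the population is settled by the plan and not at programming.
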